11.2.3.5. Duration of overall process

The duration between cord blood collection and centrifugation expressed in hours will be computed using and storage date and time (fields [CORD_BL].[TBFR_DT] and [CORD_BL].[TBFR_HH] and [CORD_BL].[TBFR_MM]).

11.2.4. Medical attendance – Health care utilization

The following endpoint categories of healthcare utilization have been defined at each examination visit in MEDICALATTENDANCE screen:

- Outpatient visit: if [MED_ATD]. [MEDATD] = "General Practitioner" OR "Outpatient clinic"
- Emergency Room visit: IF [MED_ATD]. [MEDATD] ="Emergency Room"
- Inpatient Admission (non intensive care): IF [MED_ATD]. [MEDATD] = "Inpatient clinic (Hospitalisation) Medium care" OR "Inpatient clinic (Hospitalisation) Regular care" OR "Inpatient clinic (Hospitalisation) nebulization"
- Inpatient Admission with intensive care: IF [MED_ATD]. [MEDATD] = "Inpatient clinic (Hospitalisation) Intensive care" OR "Inpatient clinic (Hospitalisation) Ventilation "
- No consultation other than site clinic: IF [MED_ATD]. [MEDATD] = . (missing)
- Other

In case several medical attendances are reported for the same event, the worst event will be considered for the analyses.

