9. STATISTICAL METHODS (AMENDED 15-DEC-2017)

9.1. Endpoints for the *Primary Study* (first 2 years)

9.1.1. Co-Primary endpoints

- Occurrence of RSV as confirmed by RT-qPCR.
- Occurrence of different types of healthcare utilization*.

* Healthcare utilization includes primary, secondary and tertiary care settings such as self-care with OTC drugs, GP visits, ER visits, hospital visits, etc.

- Occurrence of LRTI/severe LRTI as classified by the LRTI case definition and severity scale.
- Occurrence of LRTI/severe LRTI as classified by the existing comparator LRTI case definition by WHO and by Nokes et al.

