9.7.1. Co-primary objectives

• To determine the total health burden of RSV-associated RTI with a suspicion of involvement of the lower respiratory tract.

Incidence rates will be calculated as the number of RSV-associated RTI with a suspicion of involvement of the lower respiratory tract over the number of children-years observations, overall and by subgroups.

Descriptive statistics of the different types of healthcare utilization from all healthcare settings will be provided (proportions, duration, etc.) among RSV-associated RTI with a suspicion of involvement of the lower respiratory tract, overall and by subgroups.

• To assess the performance of the LRTI case definition and severity scale for RSV-associated cases.

Incidences rates will be calculated as the number of RSV-associated LRTI/severe LRTI as classified by the LRTI case definition and severity scale and also as classified by the comparator case definitions (WHO and Nokes, et al [Modjarrad, 2016; Nokes, 2004]), over the number of children-years observations, overall and by subgroups.

Descriptive statistics of the different types of healthcare utilization will be provided (proportions, duration, etc.) among RSV-associated LRTI/severe LRTI as classified by the LRTI case definition and severity scale and also as classified by the comparator case definitions (WHO and Nokes, *et al* [Modjarrad, 2016; Nokes, 2004]), overall and by subgroups.

Statistical analysis of agreement will be performed to compare the different case definitions of RSV-associated LRTI/severe LRTI and key healthcare utilization and health outcomes (the hospitalization status, (P) intensive care unit [ICU] attendance, clinical diagnosis of bronchiolitis or pneumonia, death) overall and by age categories.

Table 15 Comparison of two classifications for severe/Non-severe LRTI

RSV-associated cases		Classification of reference (severe/Non-severe)		
		Hospitalized	Not hospitalized	
Alternative classification (severe / Non-severe)	Severe LRTI (LRTI case definition and severity scale)	True positive (TP)	False positive (FP)	
	Non-severe LRTI (LRTI case definition and severity scale)	False negative (FN)	True Negative (TN)	

2x2 contingency tables such as Table 15 will be provided and the following measures of agreement (with 95% CI) will be calculated:

- Sensitivity: TP/ (TP+FN)
- Specificity: TN/ (TN+FP)
- Positive predictive value (PPV): TP/ (TP+FP)
- Negative predictive value (NPV): TN/ (TN+FN)

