4. ENDPOINTS

4.1. Co-primary endpoints

- Occurrence of RSV as confirmed by RT-qPCR.
- Occurrence of different types of healthcare utilization*.

* Healthcare utilization includes primary, secondary and tertiary care settings such as self-care with OTC drugs, GP visits, ER visits, hospital visits, etc.

- Occurrence of LRTI/severe LRTI as classified by the LRTI case definition and severity scale.
- Occurrence of LRTI/severe LRTI as classified by the existing comparator LRTI case definition by WHO and by Nokes et al.

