6.7. Health care utilization analysis

For this objective, the analysis will be based on PPS.

Descriptive statistics of the different types of healthcare utilization associated with disease severities will be produced by age interval and by country.

Please note that the heath care utilization reported here are only including medical care that subject were seeking outside the site clinics.

The number and percentage of all episodes(including recurrent) leading to outpatient visit, emergency room visit, Inpatient Admission-Non-Intensive Care, Inpatient Admission-ICU and No physician consultation outside site clinic will be displayed according for WHO RSV LRTI and WHO RSV severe LRTI cases.

The distribution (means and SD) of the number of days the usual care giver or another person took care of the child without missing work, the number of days a person had to stay home specifically because of the illness instead of going at work, and the number of days a person was hired to care for the child specifically because of the illness, will be displayed according to WHO RSV LRTI and WHO RSV severe LRTI status.

For clarity the type of health care utilization for RSV disease episodes is summarised in the table below showing endpoints and analytic methods.

200150 (EPI-RSV-005 BOD)

Statistical Analysis Plan Amendment 1 Final

Subgroup	Case definition	Endpoints	Event considered
By age categories and	WHO RSV LRTIWHO RSV severe	The number and proportion of episodes classified by	All events including
by country	LRTI	Outpatient visit	recurrent
		Emergency Room visit	oronto
		Inpatient Admission (non intensive care)	
		Inpatient Admission (intensive care)	
		No consultation other than site clinic	
		1 Other	
		• By episodes the mean and SD of:	
		The number of days the usual care giver or another person took care of the child without missing work	
		The number of days a person had to stay home specifically because of the illness instead of going at work	
		The number of days a person was hired to care for the child specifically because of the illness	

Table 13Summary of health care utilization for RSV disease episodes for
primary objectives

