12.4. Primary health care utilization analysis

12.4.1. (PO1) To determine the total health burden* of RSV-associated RTI with a suspicion of involvement of the lower respiratory tract

Template 18 Number and percentage of healthcare utilization (supplementary to care provided by study sites) for all episodes of [WHO RSV LRTI, WHO RSV severe LRTI], by age interval [overall, in <each country>] (PPS)

Age interval (Months)	Characteristic	Ν	n	%
0-5	Outpatient visit			
	Emergency room visit			
	Inpatient Admission- Non-Intensive Care			
	Inpatient Admission-with intensive			
	care			
	No consultation other than site clinic			
	Other			
6-11				
0-11				
12-23				
0-23				

N = total number of episodes for the age interval considered

n/% = number / percentage of episodes in a given category with the most intense level of care utilized

Template 19 Frequency of type of caregiver and number of days care utilized per caregiver for episodes of [WHO RSV LRTI, WHO RSV severe LRTI], all episodes considered, by age interval [overall, in <each country>] (PPS)

				Number of days care per caregiver *							
Age interval (Months)	Characteristics	N	n (%)	Mean	SD	Median	Min	Max			
0-5	Usual care giver or another person took care of the child without missing work										
	A person had to stay home specifically because of the illness instead of going at work										
	A person was hired to care for the child specifically because of the illness										
6-11											
0-11											
12-23											
0-23											

N = number of episodes for the age interval considered

n/% = number of episodes for which a caregiver of a given category is provided

SD = Standard deviation

*An event will be taken into account for the calculation of the duration only if type of utilization is reported for that event. The denominator is the n.

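### The healthcare-utilization table counts each RSV LRTI episode only at its highest level of care, so it does not report the stated co-primary endpoint, and the omission of OTC self-care is not declared

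*SAP*

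**What the plan says.** Protocol 9.1.1 lists as a co-primary endpoint "Occurrence of different types of healthcare utilization". SAP 4.1 repeats it and spells out the scope: "Healthcare utilization includes primary, secondary and tertiary care settings such as self-care with OTC drugs, GP visits, ER visits, hospital visits, etc". Protocol 9.7.1 plans the analysis in the same terms: "Descriptive statistics of the different types of healthcare utilization from all healthcare settings will be provided (proportions, duration, etc".

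SAP 6.7 describes the output as "The number and percentage of all episodes(including recurrent) leading to outpatient visit, emergency room visit" and so on up to intensive care, by age and country, for WHO RSV LRTI and WHO RSV severe LRTI. It limits the table to care sought outside the study-site clinics.

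SAP 11.2.4 derives the categories: outpatient (GP or outpatient clinic), emergency room, inpatient non-intensive, inpatient intensive, no consultation, and an undefined 'Other'. It then reduces each episode to one of them: "In case several medical attendances are reported for the same event, the worst event will be considered for the analyses". The footnote to Template 18 (SAP 12.4.1) agrees, defining its entries as "number / percentage of episodes in a given category with the most intense level of care utilized". The no-consultation category is derived from an empty field: "No consultation other than site clinic: IF [MED_ATD]. [MEDATD] = . (missing").

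SAP section 9 declares the new category list. It mentions neither the one-level-per-episode rule nor the loss of OTC self-care.

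**The concern.** Utilization is one of the two components of the health burden in the first co-primary objective, and Template 18 is its main output. The endpoint and SAP 6.7 ask how often each type of care was used. The derivation and the template answer a different question: the highest level each episode reached. The two agree only if no episode involves more than one level of care.

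That is unlikely here. SAP 11.2.4 defines attendance at each examination visit, and SAP 11.2.1.11 merges worsening visits into the initial episode. Protocol 6.5.14 foresees children with severe symptoms being redirected to urgent care, so an emergency visit followed by admission is a foreseeable path. The loss depends on how often families pass through primary or emergency care before admission. Results are shown by country, so differences in the outpatient and emergency rows would partly reflect referral pathways.

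OTC self-care is a separate gap. It is named in the endpoint, and Protocol 6.5.14 includes it in the utilization recorded from the diary card, yet no SAP category holds it. An episode treated only with OTC drugs would fall into 'no consultation' or 'Other'.

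**Working it through.** The documents give no expected utilization proportion, so there is no figure of the plan's own to reproduce. The direction follows from the rule; the size can only be illustrated.

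**Direction.** For any type of care, the episodes where it is the highest level are a subset of the episodes where it was used at all.

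- Highest-level count ≤ any-use count, with strict inequality as soon as one episode also has a higher level.
- Intensive care is at the top and is unaffected.
- The two inpatient rows added together still give any admission; only the non-ICU row alone falls short when intensive care follows.
- The shortfall lies in outpatient/GP and emergency care.

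**Size, per N = 1000 RSV LRTI episodes.** Protocol 9.3 expects the RSV LRTI rate to be 8 times the hospitalization rate. Taking that ratio as the admitted share of episodes (an assumption), H = 1000/8 = 125 are admitted and n = 875 are not. Four further inputs are assumed:

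- a: share of non-admitted episodes whose highest level is outpatient/GP, 20–60%
- e: share of non-admitted episodes whose highest level is emergency, 5–15%
- s: share of admitted episodes that also had outpatient care, with the same share for emergency care, 0–90%
- t: share of emergency-highest episodes that also had outpatient care, 0–50%

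Formulas:

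- Outpatient: reported = n·a; any use = n·a + n·e·t + H·s
- Emergency: reported = n·e; any use = n·e + H·s
- Share lost = 1 − reported / any use

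| Case | Outpatient reported / any use | Lost | Emergency reported / any use | Lost |
|---|---|---|---|---|
| No overlap (s = 0, t = 0; a = 40%, e = 15%) | 350 / 350 | 0% | 131.25 / 131.25 | 0% |
| Middle (a = 40%, e = 15%, s = 50%, t = 0) | 350 / 412.5 | 15% | 131.25 / 193.75 | 32% |
| Largest outpatient loss (a = 20%, e = 15%, s = 90%, t = 50%) | 175 / 353.1 | 50% | 131.25 / 243.75 | 46% |
| Largest emergency loss (a = 20%, e = 5%, s = 90%, t = 0) | 175 / 287.5 | 39% | 43.75 / 156.25 | 72% |

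Middle case: H·s = 125 × 0.5 = 62.5, so 62.5/412.5 = 15% and 62.5/193.75 = 32%. Largest outpatient loss: 175 + 131.25 × 0.5 + 125 × 0.9 = 353.1.

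**Blank field.** If a share T of episodes truly had an outside consultation and a fraction m of those went unrecorded, the reported no-consultation share is 1 − T + T·m. With T = 60% and m = 10% (both assumed) this is 40% + 6% = 46% against a true 40%. With m = 0 there is no error. The recorded outpatient and emergency counts are the same whether blanks are labelled 'none' or 'missing'.

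**The case against.** Template 18 is honestly labelled. Its footnote says that episodes are counted at the highest level of care, and a labelled hierarchy is a valid description in an analysis without hypothesis tests. This stands, and it means the table is not wrong in itself. It does not remove the conflict with the endpoint and SAP 6.7, or the absence of any other table of GP and emergency use.

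A reader might infer that hospital burden is under-counted too. The documents do not support this. RSV hospitalization is derived from any inpatient attendance (SAP 11.2.1.8), and SAP 6.6.1 gives it its own incidence and Kaplan-Meier output. The highest-level rule does not affect those results.

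A reader might also infer that the OTC gap and the blank rule lower the GP and emergency counts. They do not: the first concerns self-care only, and the second concerns only the label on episodes with no recorded attendance. Whether the blank rule overstates 'no consultation' depends on the eCRF. A blank may be the designed entry when no care was sought, and Protocol 6.5.15 and 6.5.18 call for diary data to be confirmed with providers. This is a point to check, not an established bias.

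On OTC, SAP 6.7 can be read as excluding self-care by restricting the table to medical care sought outside the site clinics, and the list in section 9 shows no such category. But SAP 4.1 still names it, and no sentence says that it was dropped.

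Finally, because Protocol 9.7.1 mentions duration, a reader might take the hospitalization durations in SAP 11.2.1.8 as length of stay. That derivation is in a figure not available here, and 11.2.1.9 ties the RSV LRTI hospitalization duration to the LRTI event, so it may be illness duration.

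**Conclusion.** The concern holds for the highest-level rule. Template 18 will not report the co-primary endpoint as defined, nor what SAP 6.7 describes, and section 9 does not declare the change. Outpatient/GP and emergency occurrence, and non-ICU inpatient occurrence when intensive care follows, are reported at or below their true values. They are strictly below whenever an episode has more than one level of care.

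The direction is certain from the text; the size is not. The 0–50% and 0–72% ranges, and the middle case of 15% and 32%, rest on assumed overlap shares and on carrying the 8-to-1 rate ratio over to episodes. The true loss could be close to zero.

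The undeclared omission of OTC self-care is a second, smaller defect. The blank rule is a query. The analysis is descriptive, the table is labelled and hospitalization is analysed separately, so this should be fixed but does not rank as a must-fix.

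**What to change.** - **SAP 11.2.4:** derive a yes/no flag per episode for each recorded setting: GP/outpatient, emergency, inpatient non-ICU, inpatient ICU.
- **Template 18:** report n (%) for each flag as non-exclusive rows. Keep the present highest-level split as a second panel, and state its ranking, including where 'Other' falls.
- **OTC self-care:** add a row if the diary and eCRF data allow it. If not, declare the omission in SAP section 9.
- **Blank attendance field:** check the eCRF instructions. If a blank is not the designed entry for no care sought, show 'missing' separately from 'no consultation'.
- **Length of stay:** do not take it from the durations in 11.2.1.8 without confirming what they measure.

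The flags use attendance values that 11.2.4 already reads, so the cost is some wording and minor programming. The OTC row and the none-versus-missing split depend on data that the documents do not show to exist. The downside is that first-panel percentages no longer sum to 100%, which needs a footnote.

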12. ANNEX 3: STUDY SPECIFIC MOCK TFL

12.1. Descriptive analysis

12.1.1. Disposition of subjects

Template 1 Number of subjects enrolled into the study and the number of subjects excluded from PPS analyses with reasons for exclusion – [overall] and [by country]

	0١	/era		A	R		В	D		С	Α		F	I		Η	Ν		S	Α		Т	Η		U	S
Title	n	s	%	n	S	%	n	S	%	n	S	%	n	S	%	n	S	%	n	S	%	n	S	%	n	s %
Total screened subjects: subjects who signed the ICF			-																							
Screen failures			-																							
Subjects excluded from all stat analysis (code 900)																										
Total cohort			100																							
Protocol violation (inclusion / exclusion) (code 2010)			-																							
PPS cohort			XX.X																							
Subjects not randomized to blood sampling visit (code 2500)																										
Serological results were not available for subjects at visit 3 who had a BS as randomized from SBIR (code 2502)																										
Total sub-cohort																										
Blood sample taken but: non- compliance with blood sampling schedules (code 2501)																										
PPS sub-cohort											1			1												

n= number of subjects with the elimination code assigned excluding subjects who have been assigned a lower elimination code number

s = number of subjects with the elimination code assigned

%= percentage of subjects in the PPS relative to the Total cohort.

AR = Argentina

BD = Bangladesh

CA = Canada

FI = Finland

HN = Honduras

SA = South Africa

TH = Thailand

US = US

12.1.2. Screening/study conclusion

	Tot N =	al	AR N =		BD N =		CA N =		FI N =		HN N =		SA N =		TH N =		US N =	
	n	%	n	%	n	%	n	%	n	%	n	%	n	%	n	%	n	%
Screening failure																		
Yes																		
No																		
Reason of screening failure																		
Eligibility criteria not fulfilled																		
Protocol violation																		
Consent withdrawal, not due to a Serious Adverse Event																		
Migrated / moved from the study area																		
Lost to follow-up																		
Non-serious AE																		
Serious Adverse Event related to study participation																		
Other																		
NA																		

Screening conclusion – overall and by country (Screened cohort) Template 2

N = total number of subjects

n/% = number / percentage of subjects in a given category

AR = Argentina

BD = Bangladesh CA = Canada

FI = Finland

HN = Honduras

SA = South Africa

TH = Thailand

US = US

200150 (EPI-RSV-005 BOD)

Statistical Analysis Plan Amendment 1 Final

Template 3 Number of subjects completing the primary study and number withdrawn with reasons for withdrawal – overall and by country (PPS)

	Tota	al	AR		BD		CA		FI		HN		SA		TH		US	
	N =		N =		N =		N =		N =		N =		N =		N =		N =	
	n	%	n	%	n	%	n	%	n	%	n	%	n	%	n	%	n	%
Number of subjects																		
completing the primary																		
study																		
Number of subjects withdrawn																		
Reasons for withdrawal																		
Consent withdraw al, not due																		
to a Serious Adverse Event																		
Migrated/moved from the																		
study area																		
Lost to follow-up																		
Non-Serious AE																		
Serious Adverse Event related																		
to study participation																		
Other																		

N = total number of subjects

n/% = number / percentage of subjects in a given category

AR = Argentina

BD = Bangladesh

CA = Canada

FI = Finland

HN = Honduras

SA = South Africa

TH = Thailand

US = US

12.2. Demographics/Birth status

12.2.1. Demographics at birth

Template 4 Summary of demographic and baseline characteristics of subjects – overall and by country (PPS)

	Total		AR		BD		CA		FI		HN		SA		TH		US	
	N =		N =		N =		N =		N =		N =		N =		N =		N =	
	Value	%	Value	%	Value	%	Value	%	Value	%	Value	%	Value	%	Value	%	Value	%
	or n		or n		or n		or n		or n		or n		or n		or n		or n	
Age of mother																		
at delivery																		
[years]																		
18-27																		
28-37																		
>=38																		
Singleton or multiple pregnancy																		
Singleton																		
Multiple																		
Caesarian section																		
Yes																		
No																		
Presence of																		
meconium in																		
the amniotic																		
fluid																		
Yes																		
No																		
Unknown																		
Gestational																		
age at birth (Weeks)																		
≤ 28																		
29-32																		
33-36																		
≥ 37																		
Gender of new born																		
Male																		
Female																		
Missing																		
Born in																		
transmission																		
season																		
Yes																		
No																		
Predominant																		
geographic																		
ancestry	 																	
Atrican Heritage		1		1		1		1		1								

200150 (EPI-RSV-005 BOD) Statistical Analysis Plan Amendment 1 Final

	Total				DD		C 4			ISU		ary		n P		ne		Ilai
					עם								5A N -				U3	
	N =	0/	N =	0/	N =	0/	N =	0/	N =	0/								
	value	%	value	%	value	%	value	%	value	%								
/ African					0111				0111								0111	
American																		
American Indian																		-
American mulan																		
Native																		
Asian –																		
Central/South																		
Asian Heritage																		
Asian – East																		
Asian Heritage																		
Asian –																		
Japanese																		
Heritage																		
Asian – South																		
East Asian																		
Heritage																		
Native Hawaiian																		
or Other Pacific																		
Islander																		
White – Arabic																		
/North African																		
Heritage																		
White –																		
Caucasian /																		
European																		
Heritage																		
Latino / Mestizo																		
Other																		
Length [cm]																		
Mean																		
SD																		
Median																		
Minimum																		
Maximum																		
Missing																		
Weight [kg]																		
<1																		
1_1 499																		-
1 5_1 000																		
2_2 /00																		
>25																		
=2.J																		
5 minutes																		
nyai suure		-		-														\vdash
1.6		+																\vdash
4-U >-7		-				-						-						\vdash
/		-		-														\square
Dreast reeding		-																\vdash
res		-		-														\square
INO		-		-														\square
Missing			1	1	1	1												

200150 (EPI-RSV-005 BOD) Statistical Analysis Plan Amendment 1 Final

	Tatal						C A			.1511		aly	515 FIA	 		me		IIai
	Total		AR		BD		CA				HN		5A		IH		05	
	N =	0/	N =	0/	N =	0/	N =	0/	N =	•	N =	•	N =	0/	N =	•	N =	•
	Value	%	Value	%	Value	%	Value	%	Value	%	Value	%	Value	%	Value	%	Value	%
D (())	or n		or n		or n		or n		orn		or n		orn		orn		orn	
Breastfeeding																		
duration*																		
Mean																		
SD																		
Median																		
Minimum																		
Maximum																		
Missing																		
Highest																		
education level																		
of the mother:																		
Higher /																		
universitv																		
education																		
Yes																		
No		1		1		1		1										
Missina																		
Highest																		
education level																		
of the father																		
Higher /																		
university																		
education																		
Voc																		
No																		
Missing																		
Number of																		
Number of																		
people living in																		
the nousehold																		
1-3																		
4-0																		
>=/																		
Mean																		
SD																		
Median																		
Minimum																		
Maximum		1				1		1										
Missing																		
Number of																		$\left \right $
other children (
<18 years old)																		
living in the																		
household at		1				1		1										
Month 3																		
0																		
1-2																		
>=3																		
Mean				1														
SD				1														
Median																		
Minimum																		

200150 (EPI-RSV-005 BOD)

												. 4	.00130		1-130	v-(100 DC)))
									Stat	isti	cal An	aly	sis Pla	n A	\mend	me	nt 1 Fi	nal
	Total		AR		BD		CA		FI		HN		SA		TH		US	
	N =		N =		N =		N =		N =		N =		N =		N =		N =	
	Value	%	Value	%	Value	%	Value	%	Value	%								
	orn		orn		orn		orn		or n		or n		orn		orn	1	orn	
Maximum																		
Missing																		
Subiect in																		
regular close																		
contact with																		
toddlers at																		
Month 3																		
Yes																		
No																		
Missing																		
The child live																		
in a																		
surrounding																		
where people																		
smoke daily at																		
Month 3																		
Yes																		
No																		
Missing						1		1										

N = total number of subjects

n/% = number / percentage of subjects in a given category

Value = value of the considered parameter

SD = standard deviation

AR = Argentina

BD = Bangladesh

CA = Canada

FI = Finland

HN = Honduras

SA = South Africa

TH = Thailand

US = US

Transmission season:

October to March for Argentina, South Africa;

April 2014 to September 2014 for Canada, Finland, United states;

All year long for Bangladesh, Honduras, Thailand

Note:

Gender information reported herein was collected during the ongoing extension study, causing some missing data Breastfeeding duration was provided for subjects who breastfed

200150 (EPI-RSV-005 BOD)

Statistical Analysis Plan Amendment 1 Final

Template 5 Summary of demographic characteristics of subjects with blood sample – overall and by time point (PPS sub cohort)

	Mont N =	h 2	Month N =	า 4	Month N =	6	Month N =	12	Month N =	18	Month N =	24
	n	%	n	%	n	%	n	%	n	%	n	%
Country												
Argentina												
Bangladesh												
Canada												
Finland												
Honduras												
South Africa												
Thailand												
US												
Gender of new born												
Male												
Female												
Missing												
Gestational age at birth (weeks)												
≤ 28												
29-32												
33-36												
≥ 37												

N = total number of subjects at each timepoint

n/% = number / percentage of subjects in a given category

Value = value of the considered parameter

Note:

Gender information reported herein was collected during the ongoing extension study, causing some missing data

Template 6 Number of subjects by center (Total enrolled cohort)

Center	Total N =	
	n	%

N = number of subjects of total enrolled cohort

n = number of subjects enrolled for a given center

Center = GSK biologicals assigned center number

% = n/N

- 12.3. Incidence
- 12.3.1. Primary incidence analysis
- 12.3.1.1. (PO1) To determine the total health burden* of RSV-associated RTI with a suspicion of involvement of the lower respiratory tract
- Template 7 Incidence rate of first episode of [RSV RTI with suspicion of involvement of LRT, WHO RSV LRTI, WHO RSV severe LRTI, RSV hospitalization, WHO RSV LRTI hospitalization, WHO RSV severe LRTI hospitalization], by age interval overall and by country (PPS)

						95% exact Cl	
Country	Age interval (Months)	Total number of subjects	Total number of first episode	Total number of person- years	Incidence rate (100 person- years)	LL	UL
Overall	0-5						
	6-11						
	0-11						
	12-23						
	0-23						
<each country=""></each>							1

Incidence rate computed using the number of first episode as numerator and the total number of person-years over the entire follow-up as denominator

CI=confidence interval, LL, UL for incidence = Exact 95% Lower and Upper confidence limits

Template 8 Incidence rate of first episode of WHO RSV LRTI, WHO RSV severe LRTI, RSV hospitalization, by age interval – by country (PPS)

		95% exact CI						
Country	Age interval	Episodes	Total number of subjects	Total number of first episode	Total number of person- years	Incidence rate (100 person- years)	LL	UL
<each country ></each 	0-11 months	WHO RSV LRTI						
		WHO RSV severe LRTI						
		RSV hospitalization						
	12-23 months	WHO RSV LRTI						
		WHO RSV severe LRTI						
		RSV hospitalization						

Incidence rate computed using the number of first episode as numerator and the total number of person-years over the entire follow-up as denominator

CI=confidence interval, LL, UL for incidence = Exact 95% Lower and Upper confidence limits
Statistical Analysis Plan Amendment 1 Final

Template 9 Proportion affected by at least one episode of [RSV RTI with suspicion of involvement of LRT, WHO RSV LRTI, WHO RSV severe LRTI, RSV hospitalization, WHO RSV LRTI hospitalization, WHO RSV severe LRTI hospitalization] by age interval – overall and by country (PPS)

					95% e	xact Cl
Country	Age interval (Months)	Total number of subjects at birth	Total number of subjects affected	Proportion affected	LL	UL
Overall	0-5					
	6-11					
	0-11					
	12-23					
	0-23					
<each country=""></each>						

Proportion affected computed using the number of subjects experiencing at least one episode as numerator and the total number of subjects at start of the age interval as denominator.

CI=confidence interval, LL, UL for proportion affected = Exact 95% Lower and Upper confidence limits

Template 10 Proportion affected by at least one episode of WHO RSV LRTI, WHO RSV severe LRTI, RSV hospitalization, by age interval – overall and by country (PPS)

						95% e	exact CI
Country	Age interval (Months)	Episodes	Total number of subjects at birth	Total number of subjects affected	Proportion affected	LL	UL
<each country ></each 	0-11	WHO RSV LRTI					
,		WHO RSV severe LRTI					
		RSV hospitalization					
	12-23	WHO RSV LRTI					
		WHO RSV severe LRTI					
		RSV hospitalization					

Proportion affected computed using the number of subjects experiencing at least one episode as numerator and the total number of subjects at start of the age interval as denominator.

CI=confidence interval, LL, UL for proportion affected = Exact 95% Lower and Upper confidence limits

200150 (EPI-RSV-005 BOD)

Statistical Analysis Plan Amendment 1 Final

Template 11 Incidence proportion of first episode of [RSV RTI with suspicion of involvement of LRT, WHO RSV LRTI, WHO RSV severe LRTI, RSV hospitalization, WHO RSV LRTI hospitalization, WHO RSV severe LRTI hospitalization] by monthly age interval in first six month of life– by country (PPS)

					95% exa	act Cl
Country	Age interval (Months)	Total number of subjects at risk	Total number Of first episode	Incidence proportion	LL	UL
<each country=""></each>	Less than 1					
	1					
	2					
	3					
	4					
	5					

Incidence proportion computed using the number of first episode as numerator and the total number of subjects at risk as denominator.

Note that subjects who have presented a first episode in a previous category are not considered in the subsequent age categories.

CI=confidence interval, LL, UL for incidence proportion = Exact 95% Lower and Upper confidence limits

Template 12 Incidence rate of first episode of [WHO RSV LRTI, WHO RSV severe LRTI and RSV hospitalization] in first 6 months of life with <=3 months or >3 months follow up in the transmission season – by country (PPS)

						95%	exact CI
Country	Follow up in transmission season	Total number of subjects	Total number of first episode	Total number of person- years	Incidence rate (100 person- years)	LL	UL
<each country<="" td=""><=3 months							</each>	<=3 months						
>	>3 months						

Incidence rate computed using the number of first episode as numerator and the total number of person-years over the entire follow-up period as denominator

Transmission season:

October to March for Argentina, South Africa;

April 2014 to September 2014 for Canada, Finland, United states;

All year long for Bangladesh, Honduras, Thailand

CI=confidence interval, LL, UL for incidence = Exact 95% Lower and Upper confidence limits

